1.1.2. Estimand

Treatment condition:

- Part 1 and 2: Ascending single and multiple doses of GSK3965193 and Placebo

Population:

- Part 1 and Part 2: Healthy participants

Estimand			
Estimand Category	Variable/Endpoint	Intercurrent Strategy	Population Level Summary Measure
To assess the safety and tolerability of oral administration of GSK3965193	
 Incidence of AEs, SAEs, and AEs leading to withdrawal Incidence of clinically significant laboratory parameters (haematology, clinical chemistry, urinalysis), vital signs, and cardiac parameters (electrocardiogram [ECG]), and sensory nerve conduction (Parts 2) 	
Part 1: Single dose. No intercurrent event identified
 
Parts 2: Intercurrent event of discontinuation of, interruption in, and non-adherence to GSK3965193 will be handled by treatment policy strategy, i.e., regardless of the intercurrent event occurring
	
Categorical variables: proportions
 
Continuous variables: mean, standard deviation, median, minimum, and maximum

1.2. Study Design

CCI

CCI

CCI

CCI

CCI

2. STATISTICAL HYPOTHESES

The primary objectives of parts 1 and 2A of this study are to assess the safety and tolerability of single and repeat ascending doses of GSK3965193 in healthy participants and the primary objective of part 2B is to evaluate the food effect of GSK3965193 CCI of single dose 1 with fed and fasted condition and comparison of GSK3965193 CCI of single dose 1 and GSK3965193 CCI of single dose 2 both in fasted conditions.

No formal hypotheses will be tested. However, wherever appropriate, an estimation approach will be used, and point estimates and confidence intervals (CIs) will be constructed.

2.1. Multiplicity Adjustment

Not Applicable

3. ANALYSIS SETS

Analysis Set	Definition / Criteria	Analyses Evaluated
All Screened Subject	
 All participants who were screened. 
Note: screening failures and participants screened but never enrolled into the study (Met eligibility but not needed) are included in this analysis set.
	
 Study Population
Enrolled	
 All participants who passed screening and entered the study. 
Note: screening failures (who never passed screening even if rescreened) and participants screened but never enrolled into the study (Met eligibility but not needed) are excluded
	
 Study Population

Analysis Set	Definition / Criteria	Analyses Evaluated
	from the Enrolled analysis set as they did not enter the study.	
Randomized	
 All participants who were randomized and may or may not have received study treatment. 	
 Study Population
Safety	
 All participants who received at least 1 dose of study treatment. This population will be based on the treatment the participant received. 	
 Safety Study Population
Pharmacokinetic (PK) Concentration	
 All participants in the Safety population who received an active study treatment and had at least 1 non-missing PK assessment (Nonquantifiable [NQ] values will be considered as non-missing values). This population will be used for PK concentration listing and plotting of concentration data. 	
 PK
Pharmacokinetic Parameter	
 All participants in the PK Concentration population who received an active study treatment and had at least 1 non-missing PK assessment and have evaluable PK parameters estimated. This population will be used for PK parameter listing and statistical analysis. 	
 PK

4. STATISTICAL ANALYSES

4.1. General Considerations

The study population analyses will be based on the Safety set, unless otherwise specified. Safety analyses will also be based on the safety set. PK concentration listings will be based on the PK concentration set. PK analyses will be based on PK and PK parameter set respectively.

Analysis and reporting of Part 1 data for cohorts 1 and 2 will be completed at the end of Part 1.

Also, analysis and reporting of Part 2 (2A and 2B) data for cohorts 3,4, and 5 for Part 2A and cohort 6 for Part 2B will be performed at the end of Part 2B.

4.1.1. General Methodology

Safety evaluations are planned to be descriptive in nature.

Unless otherwise specified, summary tables will provide the following descriptive statistics as a minimum:

- Continuous data:
n, mean, standard deviation (SD), median, minimum, and maximum.
- Log transformed data:
n, geometric mean, 95% confidence interval for geometric mean, SD on the log scale (SD (log)), Between subject coefficient of variation (%CV_b).
- Categorical data:
number and percentage of participants in each category.

4.1.2. Baseline Definition

Baseline is defined as the last non-missing assessment prior to first dose.

For Part 1 periods 1, 2, 3 and 4 and in Part 2B periods 1, 2, and 3 the day 1 pre-dosing assessment will be the baseline. However, if there are no pre-dose assessment collected at Day 1, the last available data from either Day -1 or screening (as schedule of assessment in each Cohort permits) will be defined as baseline. If there are no valid assessments from day 1, day -1 or screening, the baseline will be set to missing.

In Part 1 and 2B period baselines will be defined utilising the assessments taken in the specific period. Participant level baselines will also be computed and will be the means of the available period level baselines for each participant.

For Vital Signs parameters, the pre-dose data is captured as triplicate. In these cases, the baseline will be defined as the mean of the triplicate assessments.

For ECG parameters, except for QTcF, the pre-dose data is captured as triplicate. In these cases, the baseline will be defined as the mean of the triplicate assessments. In Part 1 for both cohorts 1 and cohort 2, baseline QTcF will be based on the mean of 3 pre-dose ECGs collected on Day 1 pre-dose of each treatment period.

In Part 2A, sensory nerve conduction studies at baseline will be collected twice, one at the time of screen and one prior to dosing. Mean (arithmetic mean) of two measurements will be considered as baseline.

4.2. Primary Pharmacokinetic Analyses

Then co-primary objective of Part 1 and 2A is to evaluate the Pharmacokinetic (PK) characteristics of single and repeat doses of GSK3965193, respectively.

4.2.1. Definition of endpoints

Derived Pharmacokinetic Parameters:

Pharmacokinetic parameters will be calculated by standard non-compartmental analysis according to current Clinical Pharmacology Modelling & Simulation (CPMS) working practices and using currently supported version of WinNonlin version 8.0 (or higher).

All calculations of non-compartmental parameters will be based on actual sampling times recorded during the study.

Pharmacokinetic parameters listed in the table below will be determined from the plasma concentration time data, provided there are enough evaluable data available for the calculations. If parameters cannot be determined, a 'Not done' or 'Not calculable' flag will be present in the data.

Additional plasma will also be collected in Part 1 and Part 2A (Days 1 and 14) for analysis of circulating metabolites of GSK3965193. The results will be reported separately.

Residual PK samples collected for analyses of GSK3965193 plasma concentration may also be used to evaluate GSK3965193-derived metabolites.

Table 1 Derivations for Plasma PK Parameters

Parameter	Parameter Description
Plasma PK Parameters for Part 1:	
C _{max}	Maximum observed concentration, determined directly from the concentration-time data
C _{max} /D	Maximum observed concentration normalized by dose: $\frac{C_{max}}{D} = C_{max}/Dose$
T _{max}	Time to reach C _{max} , determined directly from the concentration-time

Parameter	Parameter Description
	data
T_{last}	Time of last quantifiable concentration
$t_{1/2}$	
Apparent terminal half-life will be calculated as:
 $t_{1/2} = \ln 2 / \lambda_z$ 
Note: λ_z is terminal phase rate constant

$AUC_{(0-t)}$	Area under the concentration-time curve from time zero to the time of the last quantifiable concentration ($C(t)$) will be calculated using linear trapezoidal rule for each incremental trapezoid and the loge trapezoidal rule for each decremental trapezoid (linear up/log down calculation method in Phoenix WinNonlin).
$AUC_{(0-inf)}$	
Area under the concentration-time curve extrapolated to infinity will be calculated as:
 $AUC(0 - inf) = AUC(0 - t) + \frac{C(t)}{\lambda_z}$ 
Note: λ_z is terminal phase rate constant and $C(t)$ last quantifiable concentration

$AUC_{(0-inf)}/D$	
Area under the concentration-time curve extrapolated to infinity normalized by dose will be calculated as:
 $\frac{AUC(0 - inf)}{D} = AUC(0 - inf)/Dose$
λ_z	
λ_z is the terminal phase rate constant. A minimum number of three data points in the terminal phase will be used starting at any post-Cmax data point, only those data points that are judged to describe the terminal log-linear decline will be used in regression.
 
Note:
 
 The adjusted correlation coefficient (R^2 adjusted) in general should be greater than 0.85. Any value < 0.85 will be flagged but may be used at the PK Scientist's discretion. The interval used to determine λ_z should be equal or greater than 2-fold the estimated $t_{1/2}$ or otherwise flagged and used at the PK Scientist's discretion.

Parameter	Parameter Description
CL/F	The apparent clearance will be calculated as Dose/ AUC _(0-inf)
Plasma PK Parameters for Part 2A:	
C _τ	Trough concentration, determined directly from concentration-time data at CCI [REDACTED] for cohorts 3, 4, and 5. Additionally, it will be captured after first dose on Day 1 CCI [REDACTED] [REDACTED]
C _τ /D	Trough concentration, prior to CCI [REDACTED] normalized by dose: $\frac{C_{\tau}}{D} = C_{\tau} (Day N) / Dose$ Where, N is CC [REDACTED] for Part 2A for Cohort 3, 4 and 5
C _{max}	Maximum observed concentration, determined directly from the concentration-time data after first dose of Day 1 CCI [REDACTED] [REDACTED] for Part 2A cohort 3, 4 and 5
C _{max} / D	Maximum observed concentration after CCI [REDACTED] normalized by dose: $\frac{C_{max}}{D} = C_{max} (Day N) / Dose$ Where, N is CC [REDACTED] for Part 2A for Cohorts 3, 4 and 5
T _{max}	Time to reach C _{max} , determined directly from the concentration-time data after first dose of Day 1 and CCI [REDACTED] of Part 2A of cohorts 3, 4 and 5
AUC _τ	Area under the concentration-time curve over the dosing interval (CC [REDACTED] will be calculated after first dose of Day 1 and CCI [REDACTED] [REDACTED] for Part 2A cohorts 3, 4 and 5 using, the linear trapezoidal rule for each incremental trapezoid and the loge trapezoidal rule for each decremental trapezoid (linear up/log down calculation method in Phoenix WinNonlin).
AUC _τ /D	Area under the concentration-time curve over the dosing interval normalized by dose for the CCI [REDACTED] [REDACTED]:

Parameter	Parameter Description
	$\frac{AUC\tau}{D} = AUC\tau (Day N)/Dose$ 
Where, N is CC for Part 2A for Cohorts 3, 4 and 5

AUC _(0-t)	
Area under the concentration-time curve from time zero to the time of the last quantifiable concentration (C(t)) on after first dose on Day 1 and CCI will be calculated using linear trapezoidal rule for each incremental trapezoid and the loge trapezoidal rule for each decremental trapezoid (linear up/log down calculation method in Phoenix WinNonlin).

AUC _(0-inf)	
Area under the concentration-time curve extrapolated to infinity will be calculated as:
 $AUC(0 - inf) = AUC(0 - t) + \frac{C(t)}{\lambda_z}$ 
Note: λ_z is terminal phase rate constant and C(t) last quantifiable concentration of first dose on Day 1 and CCI

t _{1/2}	
Apparent terminal half-life will be calculated after first dosing on Day 1 CCI for Part 2A cohorts 3, 4, and 5:
 $t_{1/2} = \ln 2 / \lambda_z$ 
Note: λ_z is terminal phase rate constant

λ_z	
λ_z is the terminal phase rate constant (after dosing of Part 2A, after first dose of Day 1 CCI for cohorts 3, 4 and 5). A minimum number of three data points in the terminal phase will be used starting at any post- C_{max} data point, only those data points that are judged to describe the terminal log-linear decline will be used in regression.
 
Note:
 
 The adjusted correlation coefficient (R² adjusted) in general should be greater than 0.85. Any value < 0.85 will be flagged but may be used at the PK Scientist's discretion. 
The interval used to determine λ_z should be equal or greater than 2-fold the estimated t_{1/2} or otherwise flagged and used at the PK

Parameter	Parameter Description
	Scientist's discretion.
$R_{C\tau}$	
Accumulation ratio based on C_{τ} will be calculated as the ratio of C_{τ} for last dose (pre-dose on Day N) and C_{τ} after first dose (concentration at CC post Day 1 dose in the BID regimen):
 $RC\tau = \frac{C\tau(Day\ N)}{C\tau(Day\ 1)}$ 
Where, N is CC for Part 2A for Cohorts 3, 4 and 5

$R_{C_{max}}$	
Accumulation ratio based on C_{max} will be calculated as
 $RCmax = \frac{Cmax(Day\ N)}{Cmax(Day\ 1)}$ 
Where, N is CC for Part 2A for Cohorts 3, 4 and 5

$R_{AUC\tau}$	
Accumulation ratio based on AUC_{τ} will be calculated as:
 $RAUC\tau = \frac{AUC\tau(Day\ N)}{AUC(0 - 12)}$
Plasma PK Parameters for Part 2B:	
C_{max}	Maximum observed concentration, determined directly from the concentration-time data
$AUC_{(0-inf)}$	
Area under the concentration-time curve extrapolated to infinity will be calculated as:
 $AUC(0 - inf) = AUC(0 - t) + \frac{C(t)}{\lambda_z}$ 
Note: λ_z is terminal phase rate constant and C(t) last quantifiable concentration

T_{max}	Time to reach C_{max} , determined directly from the concentration-time data

4.2.2. Main analytical approach

The following descriptive summaries for log-transformed data will be provided for concentration data. Summaries for log transformed as well as un-transformed data will be provided for the PK parameters mentioned in Table 1. Concentrations will be listed for all participants by actual time and summarised by nominal time. All data will be summarized by dose regimen:

- **Untransformed data:** N (number of subjects in the populations), n (number of subjects used for the analysis), arithmetic mean, 95% confidence interval (CI) of arithmetic mean, standard deviation (SD), median, minimum, maximum for untransformed data.
- **Log transformed data:** N (number of subjects in the populations), n (number of subjects used for the analysis), geometric mean, 90% confidence interval (CI) of geometric mean, standard deviation (SD) of log transformed data and % Coefficient of variation between subjects (%CV_b), (except for T_{max} and t_{1/2}) for log transformed data.

4.2.3. Dose Proportionality (For Part 1 and Part 2A)

Dose proportionality for single dose will be assessed by visual inspection of dose normalised parameters for AUC_{(0-inf)/D}, and/or C_{max}/D values for Part 1 (single dose), and AUC_τ/D, and/or C_{max}/D and/or C_τ/D values for Part 2A (repeat dose) values versus dose.

Power model will also be fitted to assess dose proportionality as follows: $y = \alpha * \text{dose}^\beta$. In the log transformed manner this power model can be written as following

$$\log_e(Y) = \beta \times \log_e(\text{dose}) + \log_e(\alpha);$$

Where, y denotes the PK parameter being analysed, dose denotes the dose administered to a subject. α depends upon random subject effect and period effect and β is the coefficient of covariate log(dose). Log_e transformed data will be analysed using a mixed effect model as:

- Fixed effect: log_e(dose)
- Random effect: Subject

Data from all available doses will be considered, but if there is limited data > NQ (less than 5 participants approximately) for doses at the lower end of the dose range, these doses will be excluded from the analysis. An unstructured covariance matrix will be considered for the G matrix describing the between subject variability. If this model fails to converge, alternative covariance structures may be considered such as Variance Component, Compound Symmetry, etc. Akaike's Information Criteria (AIC) will be used to assist with the selection of covariance structure.

For Part 2A cohorts 3, 4 and 5, dose proportionality will be assessed and reported only on CCI. Hence, random effect needs not be included in the model.

Distributional assumptions underlying the model used for analysis will be examined by obtaining a normal probability plot of the residuals and a plot of the residuals versus the fitted values (i.e., checking the normality assumption and constant variance assumption of the model respectively) to gain confidence that the model assumptions are reasonable. If the assumptions are not satisfied, then alternative transformations or models can be considered.

The estimated mean slopes and 90% CIs of $\log_e(\text{dose})$ will be presented.

Note that a slope ≈ 1 implies dose proportionality.

Additionally, analysis will be performed using Analysis of Variance (ANOVA) model to assess dose proportionality. The PK parameters (AUC_τ , C_{\max}) will be dose normalised first and following a \log_e transformation, dose normalized PK parameters (AUC_τ , C_{\max} and C_τ) will be analysed separately using mixed effects model.

- Fixed effect: $\log_e(\text{dose})$
- Random effect: Subject

Data from all available doses will be considered, but if there is limited data $> NQ$ (less than 5 participants approximately) for doses at the lower end of the dose range, these doses will be excluded from the analysis. An unstructured covariance structure will be considered for the G matrix describing the between subject variability.

Distributional assumptions underlying the model used for analysis will be examined by obtaining a normal probability plot of the residuals and a plot of the residuals versus the fitted values (i.e., checking the normality assumption and constant variance assumption of the model respectively) to gain confidence that the model assumptions are reasonable.

Adjusted geometric means for each dose will be presented along with the standard errors (SE) and 90% CIs. Estimated treatment ratios to reference dose (First or lowest dose of each part) and corresponding 90% CI will also be presented.

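### The additional dose-proportionality ANOVA for Parts 1 and 2 has log dose as its only fixed effect, so as written it restates the power model and gives no separate estimate for each dose

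*SAP*

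**What the plan says.** Section 4.2.3 of the SAP for Parts 1 and 2 describes two modelled assessments of dose proportionality.

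- **Power model.** The log of the PK parameter is regressed on log dose. Log dose is the single fixed effect and is described as a covariate with coefficient beta; subject is random. For Part 2A the section adds: "Hence, random effect needs not be included in the model".
- **ANOVA.** "Additionally, analysis will be performed using Analysis of Variance (ANOVA) model to assess dose proportionality". The parameters "will be dose normalised first and following a \log_e transformation, dose normalized PK parameters" are analysed one at a time. The fixed effect is again log dose alone, and the other term is again "Random effect: Subject". The parameters named are AUC-tau, Cmax and C-tau.

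The ANOVA is to give means: "Adjusted geometric means for each dose will be presented along with the standard errors (SE) and 90% CIs". It is also to give ratios: "Estimated treatment ratios to reference dose (First or lowest dose of each part) and corresponding 90% CI will also be presented".

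Nothing in the ANOVA paragraph says that dose is a class or categorical factor.

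**The concern.** An ANOVA reported next to a power model should estimate each dose level freely, so that a plateau or jump at one dose can be seen and the straight-line assumption can be judged. That needs one mean parameter per dose. The fixed-effect line supplies only an intercept and a slope, so it conflicts with the ANOVA label and with the outputs listed below it.

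Two things are at stake. A departure at one dose would be spread over the other doses in the modelled ratios. Agreement between the two analyses would also look like corroboration when it is an identity.

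There is a second gap. Table 1 of the same SAP derives AUC-tau and C-tau for Part 2A but not for Part 1. The ANOVA parameter list therefore leaves Part 1 with Cmax only, although a reference dose is named for each part and protocol Section 9.4.7 assesses Part 1 proportionality on AUC(0-inf) as well as Cmax.

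**Working it through.** **Inputs.** The model terms come from SAP (Parts 1 and 2) Section 4.2.3. The three Part 2A cohorts come from the protocol synopsis. The doses are redacted, so every numerical example below rests on assumed values. The plan states no figure for this analysis that could be reproduced.

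**Step 1: algebra.** With Y the PK parameter, D the dose, s the subject effect and e the residual, the power model is

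log(Y) = log(alpha) + beta × log(D) + s + e.

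Subtracting log(D) from both sides gives

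log(Y/D) = log(alpha) + (beta − 1) × log(D) + s + e.

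This is the ANOVA as written: same response, same fixed effect, same random effect.

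**Step 2: what follows for the outputs.**

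- The ratio of any dose to the reference is (D/Dref)^(beta − 1).
- The standard error of its log is SE(beta) × log(D/Dref), so the test statistic is (beta − 1)/SE(beta) at every dose. Either all the 90% CIs for the ratios exclude 1 or none does.
- There are two mean parameters however many doses are studied. A class model has one per dose.

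**Step 3: noise-free illustration.** Take three equally log-spaced doses coded −1, 0, 1, equal n, and true dose-normalised values 1.00, 1.00, 0.50.

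- Slope per step = [(−1)(0) + (0)(0) + (1)(log 0.5)]/2 = −0.347.
- Reported ratios: exp(−0.347) = 0.71 and exp(−0.693) = 0.50. The middle dose shows a 29% deficit that does not exist.
- Mean of the logs = log(0.5)/3 = −0.231. The fitted geometric means are exp(−0.231 + 0.347) = 1.12, exp(−0.231) = 0.79 and exp(−0.231 − 0.347) = 0.56.

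Step size cancels, so no assumption about fold-increments is needed. Under the same spacing, true values 1, 1.8, 1 give a slope of 0 and fitted ratios 1, 1, 1: a departure at the middle dose disappears.

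**Step 4: mixed-model check.** The assumed data had 12 subjects, doses 1, 3, 10 and 30, and true dose-normalised ratios 1, 1, 1, 1.8. The SDs on the log scale were 0.25 between and 0.15 within subjects. Models were fitted by REML with a random subject intercept.

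- Power-model slope 1.16025; ANOVA-as-written slope 0.16025; difference 1. The SE (0.02657), intercept (4.4782) and log-likelihood (−12.213) are the same in both fits.
- Ratios to the lowest dose, with 90% CI:

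| Dose | True | As written | Dose as class effect |
|---|---|---|---|
| 3 | 1.0 | 1.192 (1.137–1.251) | 1.008 (0.916–1.108) |
| 10 | 1.0 | 1.446 (1.308–1.599) | 1.015 (0.923–1.116) |
| 30 | 1.8 | 1.725 (1.486–2.001) | 1.842 (1.675–2.025) |

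The three as-written ratios share one z of 6.03, as Step 2 requires. Two of their three CIs exclude the true value.

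**The case against.** The strongest reply is that a class effect was meant. The ANOVA label, the per-dose means and the ratios to a reference dose are what a factor model produces. Log dose maps one-to-one to dose level, so a programmer who declared it as a class variable would have fitted exactly the recommended model. The word covariate appears in the power-model text and is not repeated for the ANOVA. This stands as an argument about intent. It does not settle what the SAP specifies: the fixed-effect line is identical in both models, and taking logs serves no purpose for a class effect. Section 4.2.4 writes its dose term simply as dose.

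The second reply is that unconstrained information is already planned, and this stands. Section 4.2.2 summarises the Table 1 parameters by dose regimen with geometric means and 90% CIs, and Table 1 includes the dose-normalised parameters for both parts. Section 4.2.3 also calls for visual inspection of dose-normalised values against dose, including AUC(0-inf)/D, and for residual plots.

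Third, the random subject effect in the ANOVA might be read as a separate error for Part 2A. The documents do not support that: Section 4.2.3 already says the term is unnecessary there, and the ANOVA paragraph merely fails to repeat it.

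Finally, the protocol names only the power model for dose proportionality (Section 9.4.7), dose escalation uses a separate Bayesian predictive model (SAP Section 4.6), and no formal hypothesis is tested (SAP Section 2). All of this limits the consequence.

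**Conclusion.** The specification is wrong as written, with limited impact. If log dose is the continuous covariate that Section 4.2.3 describes, the ANOVA and the power model are one model, and the promised per-dose estimates all derive from one slope. The identity needs no assumption about doses or variability. The sizes (0.71 reported for a true 1.00, for example) are illustrative and rest on assumed spacing, equal n and assumed departures. The omission of AUC(0-inf)/D is plain from the parameter list and is confined to this additional analysis.

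Two stronger conclusions might be inferred and should not be drawn.

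- **That the ANOVA tables already produced for Parts 1 and 2 are wrong.** That depends on how dose was coded, which the documents do not show; display specifications sit in a separate programming document.
- **That non-proportionality would go unseen.** The by-dose summaries and plots could reveal it. Only the modelled ratios and their CIs are affected.

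**What to change.** In the ANOVA paragraph of Section 4.2.3:

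1. State dose as a categorical (class) fixed effect. Leave the power model unchanged.
2. Carry over the statement that no random effect is needed for Part 2A.
3. Add dose-normalised AUC(0-inf) for Part 1.

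Then check how dose was coded. Re-run the existing ANOVA tables only if it was continuous; the Part 1 AUC(0-inf)/D analysis is new in either case.

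**Cost.** No new data are needed. Parts 1 and 2 are complete and, according to protocol Section 9.5, already reported, so this means a SAP addendum and possibly a limited re-analysis rather than a one-line edit. Per-dose CIs will generally be somewhat wider where a straight line describes the data well. Where it does not, they need not be: in the Step 4 example the CI widens at dose 3 (upper/lower 1.108/0.916 = 1.21 against 1.251/1.137 = 1.10) but narrows at dose 30 (2.025/1.675 = 1.21 against 2.001/1.486 = 1.35).
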